8.1 Study design

This study is a PASS. This is a non-interventional registry of children treated with Norditropin® for short stature due to NS. This study aims to provide data on long-term growth evolution and safety of Norditropin® as well as HRQoL data. This registry will include the entirety of children treated with Norditropin® for short stature due to NS over the inclusion period. In consequence, this registry will enroll both patients who received Norditropin® before its marketing authorization for short stature due to NS in France and patients who received Norditropin® after its approval.

This study presents both a prospective and retrospective design. Data will be collected for 3 groups of patients:

- Incident patients: Children initiating Norditropin® upon their inclusion in the study.
- Prevalent patients:
 - Children who were already treated with Norditropin® before their inclusion in the study and finished their growth upon their inclusion. For these patients, all data will be collected retrospectively from medical records.
 - Children who were already treated with Norditropin® before their inclusion in the study and who did not finish their growth upon their inclusion. For these patients, data will be collected both retrospectively and prospectively.

HRQoL data will be collected on incident patients only.

The inclusion period will last for 24 months and patients will be followed-up for 4 years with possibility of extension for patients who did not reach AH. This will allow to provide interim results on October 2025 to the HAS.

All information will be collected as per physicians' routine of care and as this study is non-interventional, neither clinical interventions nor laboratory assessments will be imposed as per this protocol.

* The follow-up period in this study is 4 years with possibility of extension for patients who did not reach adult height.

[figure not shown]

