For incident patients, a visit schedule is provided based on the standard clinical practice for GH treatment in NS. We anticipate that each child included in this registry sees his/her enrolling physician every 6 months based on recommendations. A total of 9 visits (1 inclusion visit: D0 and 8 follow-up visits: M6, M12, M18, M24, M30, M36, M42, M48) are planned. Each visit will be allowed within one-month visit. However, no follow-up visits will be mandated by this study and the enrolling physician may not strictly comply with the schedule provided if considered as not relevant.

For prevalent patients who finished their growth upon their inclusion, all data will be collected retrospectively from medical records bi-annually from the start of Norditropin®. Visits will be referred to as V1, V2, V3... VX.

For prevalent patients who did not finish their growth upon their inclusion, data will both be collected retrospectively from medical records bi-annually from the start of Norditropin® and prospectively every 6 months following the inclusion visit.

The design of the registry is displayed in [Figure 8-1](#). This is a PASS.

Figure 8-1 Study design

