Number of modifications (change in dosage/ temporary stop)	From start of Norditropin® treatment until end of follow-up	Count of events
Reasons for treatment modifications	From start of Norditropin® treatment until end of follow-up	NA
Duration of temporary stop	From start of Norditropin® treatment until end of follow-up	Months

Title of endpoint	Time frame	Unit
Total duration of Norditropin [®] treatment	From start of Norditropin [®] treatment until end of follow-up	Years
Total cumulative dose of Norditropin [®] treatment	From start of Norditropin [®] treatment until end of follow-up	mg/kg
Other NS treatments		
Type and number of concomitant treatments	At all visits	Count of events
Type and number of concomitant treatments linked to an adverse event	At all visits	Count of events

Secondary objective-4: To describe the NS in terms of auxological characteristics, diagnosis and NS comorbidities.

The endpoints related to the secondary objective-4 are listed in [Table 6](#).

Table 6 Secondary endpoints in relation to secondary objective 4

Title of endpoint	Time frame	Unit
Auxological characteristics		
Change in weight	From start of Norditropin [®] treatment until end of follow-up	SDS
Change in body mass index (BMI)	From start of Norditropin [®] treatment until end of follow-up	Kg/m ²
Change in bone age	From start of Norditropin [®] treatment until end of follow-up	year
Change in height velocity	From start of Norditropin [®] treatment until end of follow-up	cm/year and SDS/year
Type and number of NS comorbidities	At all visits	NA

Secondary objective-5: To evaluate the evolution of Health-Related Quality of Life (HRQoL) of patients/Legally Acceptable Representative (LAR).

The endpoints related to the secondary objective-5 are listed in [Table 7](#).

Table 7 Secondary endpoint in relation to secondary objective 5

Title of endpoint	Time frame	Unit
Change in HRQoL score (PedsQL)	From start of Norditropin [®] treatment until end of follow-up	NA

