8.2.9 Assessments for safety and growth

Growth evolution

Growth evolution endpoints of GH treatment (Norditropin[®]) will be assessed by collecting height characteristics at baseline and at each follow-up visit to derive height variation in SDS, bone age, and height velocity values.

Safety

All children who received at least one administration of Norditropin[®] will be included in the evaluation for safety. All serious adverse events (SAE), serious adverse drug reactions (SADR), drug related adverse reactions (ADR) and adverse events (AE), regardless of causal relationship and seriousness criteria, and pregnancies that occur during follow-up will be recorded, reported and described.

At every follow-up visit, the enrolling physician ascertains the occurrence of ADR, SADR, SAE, AE and pregnancies. The physician must report ADR, SADR, SAE and AE using the NIS Safety Form to Novo Nordisk or to [REDACTED] within 3 calendar days of the physician's knowledge of the event. Pregnancy must be reported on the paper pregnancy form within 14 calendar days of the physician's first knowledge of the pregnancy.

Definitions and further details about ADR, SADR, SAE, AE and pregnancies are provided [10](#) section.

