8.5 Study sample size

This study will set up a registry that aims to include all eligible patients treated by Norditropin® for short stature due to Noonan syndrome.

No sample size calculation is required as this registry aims to include all patients fulfilling the sets of selection criteria defined.

According to experts' input, a maximum of 50 eligible incident patients could be included during the 24 months inclusion period. It is expected that the number of eligible patients initiating Norditropin® before 2020 would be lower since that there was no market authorisation for this indication yet and would not exceed 30 patients per year. Considering that eligible prevalent patients initiated Norditropin® from 2010, that 79% of solicited sites will be participating in the study (30 sites over 38) and that 80% of eligible patients will be included (excluding opposition, patient not regularly followed by this site), it is estimated that a maximum of 221 patients will be included in the registry.

Finally, the proportion of evaluable patients for the primary criteria (patients that have height measurements until the end of their 4 years follow-up or adult height) is planned to be 80%. Therefore, it is estimated that this study will enrol a maximum of 177 patients evaluable for the primary criteria.

The height variation (in SDS) after 4 years of treatment has been evaluated in the ANSWER® Program (observational study) at 1,14 (0,13) SDS. The change in height SDS is estimated with a 11,4% coefficient of variation (ratio of standard deviation over mean).

The following table presents the precision in primary criteria measurement (with a 2-sided 95% confidence interval (CI)) for the estimation of mean height variation in SDS considering a 20% coefficient of variation. The primary criteria will be estimated with a 2.95% precision. This high level of precision enables to perform subgroup analysis with also a satisfying precision.

Table 11 Precision of the primary criteria depending on the number of evaluable patients

Sample size	150	160	170	177	190	200
Precision for 95% CI	3.2%	3.1%	3.0%	2.95%	2.85%	2.78%

The sample size (n) is calculated based on the normal approximation using the following formula:

$$N = z_{1-\alpha/2}^2 \frac{cv^2}{\epsilon^2}$$

where:

- z is the standard normal distribution's quantile (for $\alpha=5\%$),
- CV is the coefficient of variation (20%),

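### Bone age (Table 6) is fixed as a raw change in years over a window that differs between children, so by itself it does not separate delayed, normal and advanced maturation

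*Protocol*

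**What the plan says.** Table 6 in section 8.1.1.2 names the endpoint "Change in bone age", runs it from start of Norditropin to end of follow-up and gives the unit as year. In the same table, change in weight is in SDS and height velocity is in "cm/year and SDS/year". BMI, like bone age, is left in raw units.

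The objective behind the table is descriptive: "To describe the NS in terms of auxological characteristics, diagnosis and NS comorbidities".

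Section 8.2.9 says height data will be collected at baseline and each follow-up visit "to derive height variation in SDS, bone age, and height velocity values". Table 10 (section 8.3) calls bone age a continuous variable and says no more. Table 9 schedules it at baseline, M12, M24, M36 and M48. Section 8.7.2.2 sends all secondary endpoints to the descriptive statistics of section 8.7.2. None of these places sets bone age against chronological age or elapsed time.

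The window varies by design. Section 8.1 gives 4 years of follow-up "with possibility of extension for patients who did not reach AH". For prevalent children who have finished growing, "all data will be collected retrospectively from medical records bi-annually from the start of Norditropin". Section 8.5 assumes that prevalent children started treatment from 2010 onward, and inclusion is planned for March 2022 to March 2024. Section 8.7.1 makes treatment duration a subgroup of interest because it may strongly influence auxological outcomes.

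**The concern.** Bone age is a scale in years, calibrated so that a normally maturing child moves about one unit per calendar year. A change on that scale is interpretable only next to the time over which it occurred. Table 6 gives the change without the time, and the time differs from child to child. A mean of +6 years could describe children maturing normally over 6 years, quickly over 5 or slowly over 7.

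At stake is whether the registry's bone-age result says anything about maturation during treatment. Section 8.2.9 places bone age with height SDS and height velocity under growth evolution, and a reader will want to look at them together. Height SDS is already referred to age and height velocity to time. Bone age has neither reference.

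**Working it through.** The protocol gives no figure for bone age, so there is none to reproduce. The check is an illustration.

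**Inputs**
- From the protocol: unit in years; window from treatment start to end of follow-up; 4 years, extendable, for incident children; prevalent starts from 2010. From 2010 to the planned first inclusion in March 2022 is already more than 11 years, so windows above 10 years are possible.
- Assumed, not in the protocol: a rate of bone-age advance r with mean 1 year per calendar year and a between-child SD s of 0.1 to 0.3; elapsed time T fixed at 4 years or uniform over 4–8, 4–12 or 1–12 years.

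**Step 1. Same raw change, different meaning.** Raw change D = r × T. Change in (bone age minus chronological age) = D − T. Ratio = D / T.

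| r | T (years) | D = r × T | D − T | D / T |
|---|---|---|---|---|
| 1.25 | 4 | +5.0 | +1.0 | 1.25 |
| 1.00 | 5 | +5.0 | 0.0 | 1.00 |
| 0.83 (5/6) | 6 | +5.0 | −1.0 | 0.83 |

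Likewise, r = 0.8 over 6 years and r = 1.2 over 4 years both give +4.8. At r = 1, windows of 4, 6, 8 and 12 years give +4, +6, +8 and +12.

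**Step 2. Share of the variance of D due to elapsed time.** With r independent of T and mean r = 1, Var(D) = Var(T) + s² × E(T²), so the share is Var(T) / [Var(T) + s² × E(T²)].

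Worked case, T uniform over 4–8 and s = 0.2: Var(T) = 16/12 = 1.33; E(T²) = 36 + 1.33 = 37.33; share = 1.33 / (1.33 + 0.04 × 37.33) = 1.33 / 2.83 = 47%.

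| T | s = 0.1 | s = 0.2 | s = 0.3 |
|---|---|---|---|
| 4–8 years | 78% | 47% | 28% |
| 4–12 years | 89% | 66% | 46% |
| 1–12 years | 95% | 83% | 68% |
| fixed at 4 years | 0% | 0% | 0% |

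A simulation of 200,000 children per cell gave the same values. In the last row elapsed time explains none of the spread, but the mean is still about 4 years and can be read only against the 4 years elapsed. Reading error and the plateau of bone age at skeletal maturity are not modelled.

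**Step 3. Data needed.** For readings 1 and 2, (BA2 − CA2) − (BA1 − CA1) = (BA2 − BA1) − (CA2 − CA1), where BA is bone age and CA chronological age. The last bracket is the time between the readings, so the birth date cancels. The ratio uses the same interval. Only the absolute difference at one visit needs age itself, and year of birth (Table 9) leaves that uncertain by up to a year.

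**The case against.** **The objective is only descriptive.** This stands. Secondary objective 4 does not mention accelerated maturation, and the safety topics named in section 6.2 are tumour, glucose metabolism and cardiac defects. A reader might infer that the endpoint fails a stated aim of detecting acceleration, but the protocol states no such aim. The weaker point remains: a raw change does not even describe whether maturation was delayed, normal or advanced.

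**Treatment duration is already a subgroup, and incident children share a planned M0–M48 window.** This stands in part. Both narrow the spread of elapsed time. But the subgroups still report raw years and are conditional on adequate size (section 8.7.2), and the incident window can be extended.

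**This can be left to the SAP.** A SAP, listed in Annex 1 but not shown, could add a derived variable. However, the protocol itself fixes the endpoint and its unit, and section 8.7.2.3 refers only the exploratory models to the SAP. This is a stated definition, not a detail left open.

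**Bone-age acceleration cannot be studied here.** A reader might infer this, and it is not supported. The limit lies in the endpoint as written. The scheduled bone-age readings allow the repair by one subtraction.

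**The endpoint is almost entirely elapsed time.** A figure near 90% is easy to produce. With T uniform over 2–10 years, one rate for all children and a reading error of SD 0.8 year counted once, the share is 5.33 / (5.33 + 0.64) = 89%. A change involves two readings, which gives 5.33 / (5.33 + 1.28) = 81%, and letting rates differ between children lowers it further. The documents fix none of these inputs.

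**Conclusion.** The point holds in a limited form. As fixed in Table 6, the raw change in bone age does not by itself distinguish delayed, normal and advanced maturation, because the window differs between children and no chronological reference is given. This conclusion needs only two things: that bone age advances about one year per calendar year under normal maturation, and that windows vary, which the protocol's own design ensures.

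The share of variance due to elapsed time is assumption-dependent: about 28% to 95% across the variable windows and rate SDs tried, and 0% at a fixed 4 years. It should be quoted as a range or not at all. The issue is a minor-to-moderate improvement to one descriptive secondary endpoint. No test or decision in the protocol depends on it, and it involves no clinical management rule.

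**What to change.** In Table 6, alongside or in place of the raw change, define:

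1. the change in (bone age minus chronological age), calculated as change in bone age minus elapsed time between readings;
2. the ratio of change in bone age to elapsed time between readings.

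Describe both at 12, 24, 36 and 48 months on treatment, counted from treatment start for incident and prevalent children alike, with the number of readings available at each time.

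Do not drop children because they are mature at the later reading. That would select on the outcome: the fastest-maturing children would leave first and advance would be understated. Instead, use each child's readings up to and including the first one showing skeletal maturity, and report the number mature at each time.

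The cost is one endpoint line and two simple derived variables, with no additional X-ray. The date of each reading is needed. Tables 9 and 10 list none, so confirm that the CRF (not shown) captures it. If the absolute difference at a visit is also wanted, age must be recorded more precisely than year of birth allows.

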8.1.1.3 Exploratory endpoints

Table 8 Exploratory endpoints

Title of endpoint	Time frame	Unit
Improvement of HRQoL (PedsQL score)	End of follow-up	Y/N
Height at end of follow-up >-2SDS	End of follow-up	Y/N

8.1.2 Treatment of patients

[figure not shown]
Patients will be treated with commercially available Norditropin® (NN-220; somatropin; Novo Nordisk A/S, Denmark) according to routine clinical practice at the discretion of the treating physician.

8.2 Setting

8.2.1 Sites

French reference centres for the care of short stature due to NS are gathered within the FIREENDO network. This network fulfils national missions around rare endocrine including growth and development disorders with the aim of improving the care of patients, coordinating and encouraging research and developing training and information. All the sites (reference and competence) from the FIREENDO network will be contacted to participate in the study ([Figure 8-2](#)).

Figure 8-2 French reference and competence centres of the FIREENDO network

8.2.2 Participating physicians

The population of enrolling physicians consists of paediatric endocrinologists practicing in hospital setting comprising French reference/competence centres of the FIREENDO network ([Figure 8-2](#)). A principal investigator (PI) will be designed in each site and study investigators will enrol patients into the study as per routine practice according to the inclusion and exclusion criteria defined below.

8.2.3 Study population

Planned number of patients to be included: 224

Planned number of patients to complete the study: 168

Planned time period for the study: 24 months inclusion period and 4 years follow-up (with possibility of extension for patients who did not reach their adult height)

8.2.4 Inclusion criteria

For an eligible patient, all inclusion criteria must be answered “yes”.

1. Patients with a clinical and/or genetic diagnosis of NS.
2. Patients who are treated with Norditropin[®] (already treated or initiating) and who are followed in a participating center.
3. The decision to initiate treatment with commercially available Norditropin[®] has been made by the patient/parents/Legally Acceptable Representative (LAR) and the treating physician before and independently from the decision to include the patient in this study.

8.2.5 Exclusion criteria

For an eligible patient, all exclusion criteria must be answered “no”.

1. Patients/Parents/LAR opposed to the collection and processing of their children’s medical data.
2. Mental incapacity, unwillingness or language barriers precluding adequate understanding or cooperation.

8.2.6 Rationale for selection criteria

The inclusion criteria have been defined for the purpose of developing a French registry of children treated with Norditropin[®] associated with Noonan syndrome in real clinical setting (no limitations on age neither bone age to reflect on clinical practices). The third inclusion criterion complies with the non-interventional type of the study, which must not interfere with the routine practice.

The first exclusion criterion complies with French regulatory requirements related to NIS (RIPH3), which does not require explicit consent from the patient. The second exclusion criterion prevents patients who cannot be fully informed (due to language barriers, mental incapacity etc.) to be included into the study.

Representativeness of the study population as regards to the source population (NS patients treated with Norditropin® for short stature) will be ensured at the national level by requiring from physicians to include in a consecutive and exhaustive manner all eligible patients seen during a consultation over the inclusion period .

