8.7 Data analysis

8.7.1 Definition of analysis sets

The site populations will be defined as follows:

- Contacted sites: all reference and competence centres in France will be solicited to participate in this study
- Participating sites: all sites that agreed to participate in the study
- Active sites: all sites that included at least one eligible patient

The sites main characteristics (localisation, size) will be compared to ensure that the active sites are representative at the national level.

There are 3 patients population considered in this study:

- Overall population: all patients included in the eCRF,
- Full Analysis Set (FAS): all patients included in the eCRF and meeting all selection criteria. All secondary analyses will be performed on FAS.

- Growth Analysis Set (GAS): all patients from the FAS for which the primary criteria can be evaluated, i.e. height measurements available until the end of the 5-year follow-up or until NAH is reached, whatever occurs first.

The subgroups of interest for analyses are defined as follows:

- Norditropin[®] treatment duration: depending on age of onset and age at puberty onset, the patients may have shorter or longer time under GH treatment, which may highly influence auxological outcomes
- Mutated gene: PTPN11, SOC2, other

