8.7.4 Sequential safety analysis/safety monitoring

All drug related adverse reactions (ADR), serious adverse drug reactions (SADR), serious adverse events (SAE) and adverse events (AE) will be classified and analysed from the initiation of the study drug until the end of follow-up.

Medical Dictionary for Regulatory Activities (MedDRA) version 19.1 or higher will be used for coding to "Lower Level Term (LLT)", "Preferred Term (PT)", "High Level Term (HLT)", "High Level Group Term (HLGT)" and the associated primary "System Organ Class (SOC)". CTCAE version 5 will be used to provide the grade.

AEs will be analysed as follows:

The number and percentage of patients experiencing:

- at least 1 on-treatment SAE/AE/SADR/ADR (including non-serious and serious irrespective of the relationship with the study treatment)
- at least 1 on-treatment SAE/AE/SADR/ADR related to the study treatment (including serious and non-serious AEs)
- at least 1 on-treatment serious SAE/SADR (regardless the relationship with the study treatment)
- at least 1 on-treatment serious SAE/SADR related to the study treatment
- at least 1 on-treatment SAE/AE/SADR/ADR leading to treatment discontinuation
- at least 1 on-treatment SAE/AE/SADR/ADR leading to treatment interruption/delay
- at least 1 on-treatment SAE/AE/SADR/ADR leading to dose decrease
- fatal on-treatment SAE/AE/SADR/ADR

They will be presented by SOC and preferred term.

Patient will be counted once by AE taking into account the maximum grade. The SOC/PT will be summarized (irrespective of the grade) and by maximum grade CTCAE (grade 1-2 ,3-4 and 5) as well. The incidence rate, corresponding to the number of patients experiencing at least one AE divided by the total person years of follow-up, will be calculated for each AE. A listing will be provided for fatal on-treatment AE. These analyses will be performed for the post-treatment AEs as well.

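### By the protocol's own maxima, about 86% of the registry are prevalent users who must still be in care in 2022–2024, yet height and safety are counted from treatment start and not reported by cohort

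*Protocol*

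**What the plan says.** **Entry.** Inclusion criterion 2 (Protocol 8.2.4) requires the patient to be followed in a participating centre. Section 8.2.6 says national representativeness is secured by asking physicians "to include in a consecutive and exhaustive manner all eligible patients seen during a consultation over the inclusion period". Section 5 puts that window at March 2022 to March 2024.

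**Composition.** Section 8.5 expects "a maximum of 50 eligible incident patients could be included during the 24 months inclusion period". For earlier starters it says the number "would not exceed 30 patients per year" before 2020, and that "eligible prevalent patients initiated Norditropin® from 2010". It then applies 30 of 38 sites and 80% patient inclusion to reach a maximum of 221 included, and 80% evaluability to reach 177.

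**Clock.** Tables 2 and 3 (8.1.1) run the primary and safety endpoints from the start of Norditropin. Section 8.7.4 analyses events from drug initiation and defines the incidence rate as patients with at least one event "divided by the total person years of follow-up".

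**Reporting.** Section 8.1 distinguishes three groups: incident; prevalent with growth finished (fully retrospective); and prevalent with growth ongoing (retrospective and prospective). Section 8.7.1 then introduces its list with "The subgroups of interest for analyses are defined as follows" and names only treatment duration and mutated gene. Section 8.7.2.1 describes the primary endpoint overall and by treatment duration.

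**The concern.** A child who started in 2012 and died, moved away or dropped out of care before March 2022 has no chance of being enrolled. Consecutive enrolment of those who do attend cannot repair that. The assurance in 8.2.6 is therefore not supported for earlier starters, who by the protocol's own figures make up most of the registry.

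Two results are exposed. Pooled height change from treatment start is computed mainly in children who remained in care, often for years. Incidence rates are affected if the years between treatment start and inclusion are counted as time at risk, because a death, or an event that took the child out of care, could not have been observed in those years. The Transparency Committee asked for this registry to inform long-term growth and safety, notably tumour risk, glucose metabolism and cardiac defects (6.2). A single pooled figure would not let a reader separate children observed from their first dose from those selected by still being in care.

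**Working it through.** **1. Reproduce the plan's figure.** Inputs are from 8.5: at most 50 incident patients; at most 30 per year from 2010 to before 2020, i.e. 10 years; 30/38 sites; 80% inclusion; 80% evaluable.

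- Prevalent: 30 × 10 = 300. Total eligible: 300 + 50 = 350.
- Included: 350 × 30/38 × 0.80 = 221.1, stated as 221.
- Evaluable: 221 × 0.80 = 176.8, stated as 177.

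Section 8.2.3 gives 224 and 168 instead, without a breakdown, so 8.5 is used here.

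**2. Prevalent share.** 300/350 = 85.7%.

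| | Included | Evaluable |
|---|---|---|
| Prevalent | 300 × 30/38 × 0.80 ≈ 190 | ≈ 152 |
| Incident | 50 × 30/38 × 0.80 ≈ 32 | ≈ 25 |

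(The included figures, 189.5 and 31.6, round to a sum one above 221.)

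**3. How firm is the share?**

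- The other reading that fits 221 leaves the 50 unscaled and takes 9 prevalent years: 50 + 270 × 30/38 × 0.80 = 220.5, with a prevalent share of 77%.
- Prevalent rate of 10 to 25 per year instead of 30: 67% to 83%.
- Only half of the 300 still seen in 2022–2024 (assumption): 150/200 = 75%, with a total of about 126.
- Adding 50 to 60 starters from 2020 to early 2022, whom 8.5 does not count (assumption): about 88%.
- Prevalent patients lose their majority only if fewer than 1 in 6 of the 300 are still seen (50 against 50).

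**4. Leverage on the pooled height result.** With the cited mean of 1.14 SDS and the stated 2.95% precision, the pooled half-width is 0.0295 × 1.14 = 0.034 SDS. Suppose selection shifted the prevalent mean by 0.1 SDS in either direction (an illustrative assumption). The pooled mean would move by 0.857 × 0.1 = 0.086 SDS, about 2.5 times that half-width.

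**5. Person-time.** A child who started in 2014, was included in 2022 and was followed for 4 years has 8 years before inclusion and 4 after. If all 12 years are counted, two-thirds of the time at risk could not contain a death. If events are also collected only after inclusion, the rate for any event type is 4/12, or one-third, of its value under a constant hazard.

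The protocol does not settle which time counts:

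| Points to treatment start | Points to inclusion |
|---|---|
| Table 3: time frame from start of Norditropin | 8.2.8.2: the 4-year schedule starts at inclusion |
| 8.7.4: events analysed from drug initiation | 10.1: adverse events collected after consent; Table 9 has no safety entry at baseline |

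**6. Does existing text cover it?** The weights in 8.7.2 address site activity and visit frequency; no weight can represent a patient with no visit in the window. Section 8.9.1 discusses site recruitment, consecutive enrolment and attrition after inclusion, but not loss before inclusion.

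**The case against.** Much can be said for the plan, and part of it stands.

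- A reader might infer that selected retrospective data dominate every pooled result. The documents do not support that. HRQoL is collected in incident patients only (8.1), growth-ongoing prevalent patients also contribute prospective data, and the split between the two prevalent groups is not given. The 86% counts patients, not data points. Only the treatment-start height is retrospective for every prevalent patient.
- A reader might infer that children who stopped treatment are excluded. Criterion 2 admits patients already treated, and the protocol records end of treatment and permanent stops (Tables 9 and 10). A child who stopped but is still followed may enter.
- A reader might infer that height gain is overstated. That needs poor responders to leave care more often than others. Children who reached adult height before 2022 may equally have left paediatric care. No figure in the protocol fixes the direction.
- A reader might infer that all rates are biased downward. The survivorship argument covers only fatal and follow-up-ending events; a non-fatal tumour or glucose disorder before inclusion need not prevent entry. Wider dilution requires pre-inclusion time in the denominator together with collection starting only at consent. If follow-up means time after inclusion, neither effect arises.
- The incident group is not free of selection either: the same site participation and 80% inclusion apply to it.
- Reporting by treatment duration is a partial proxy for cohort, and further displays may be left to the analysis plan. But a prevalent and an incident child can share a duration while differing in selection and data source, and 8.7.1 presents its subgroup list as defined.

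**Conclusion.** The point holds for height change and safety. On the protocol's maxima about 86% of patients are prevalent users, and they remain the majority under every variant in step 3 short of the 1-in-6 limit. Their entry depends on still being in care years after the clock for the endpoints started. The assurance of representativeness in 8.2.6 is not supported, and nothing in 8.7.2 or 8.9.1 addresses loss before inclusion.

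The size of the height bias cannot be computed from the protocol and its direction is open. Downward bias in the rates of fatal and follow-up-ending events is conditional on pre-inclusion years entering the denominator, and dilution of other rates on that plus collection from consent. Both conditions are ambiguous in the text, which is itself a reason to fix the rule now. The 86% assumes that 2010 starters are as likely to be included as 2022 starters; the attrition at issue would lower both the share and the total of 221.

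**What to change.** 1. **8.7.1 and 8.7.2.1:** add cohort (incident; prevalent, growth ongoing; prevalent, growth finished) as a prespecified subgroup for the primary endpoint and safety, with incident results always shown.
2. **8.7.4:** base incidence rates on events and person-time after inclusion, in incident and growth-ongoing patients. Report pre-inclusion events separately as retrospective data with a survivor-selection caveat. This includes all events of growth-finished patients, who have no person-time after inclusion and so no rate on this basis. Reconcile Table 3 and 8.7.4 with 8.2.8.2 and 10.1 on when collection and follow-up start.
3. **8.2.6 and 8.9.1:** replace the assurance of representativeness, and state that starters lost from care before the window cannot be represented.

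**Cost.** No extra data: additional table columns and one person-time rule. Precision falls when cohorts are shown separately. At the protocol's 20% coefficient of variation the half-width is 1.96 × 0.20/√25 = 7.8% of the mean for incident patients and 1.96 × 0.20/√152 = 3.2% for prevalent patients, against 2.95% pooled. Incidence rates will rest on fewer person-years.
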